Despite the decreases seen in IL-8 in non-pregnant adult men and women, two recent studies looking at inflammatory responses in pregnant women after influenza vaccination showed an increase in concentrations of IL-8, CRP, IL-6, TNF α , and MIF 48 hours after influenza vaccination [12, 13]. Discrepancies among studies might be caused by whether studies recruited women only [12, 13] or combined outcome data from both women and men [23]. No group has looked to see if these inflammatory responses after vaccination affect steroid hormone levels or if they have any effect on the earliest stages of pregnancy. This study is designed to explore these questions.

During our initial pilot study conducted during the 2013-2014 influenza season we examined the earliest immune responses to influenza vaccine and the potential impact on reproductive and stress hormones on women of reproductive age. Our initial findings showed no significant changes in serum hormone levels of estrogen, progesterone and cortisol after vaccination, compared with similar time points in a baseline menstrual cycle without vaccination. However, a non-significant 20% decrease in serum progesterone was observed after vaccination as compared to the non-vaccinated month[5]. Initial findings also showed increases in some cytokine levels after vaccination, compared with levels before vaccination during the vaccination menstrual cycle; cytokine levels were not assessed during the baseline menstrual cycle without vaccination[5]. Studying a larger number of women over 1 or 2 additional influenza seasons would help us better understand the effects of IIV on early immune responses and hormone levels.

III. Study Design:

A.

This is an open label study looking at the effect of influenza vaccine on cytokines and reproductive hormones. We will recruit women of reproductive age who are not on hormonal birth control, measure their cytokines and reproductive hormones for 1 month to establish a baseline, and then vaccinate them with the seasonal inactivated influenza vaccine just prior to ovulation, and follow the cytokines and reproductive hormones for the remainder of their cycle. We will use commercially available urine Luteinizing hormone (LH) strips to measure ovulation.

B. Provide a sample size and a justification as to how you arrived at that number. If you use screening procedures to arrive at a final sample a table may be helpful.

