- a. Provide sample size and a clear justification as to how you arrived at your projected sample size. We will evaluate the effect of vaccine on 90 women (see below; this includes the 30 women enrolled in the pilot study). Women who drop out before completing data collection for two menstrual cycles will be replaced. We may need to enroll up to 120 women in order to ensure a complete data set.

V. Study Procedures:

In this section, provide details of your procedures, particularly as they relate to human subjects. If this is a multi-center study, make the role of JHSPH clear. If the JHSPH will serve as **data coordinating center**, indicate in the sections below which procedures JHSPH will not be performing. Additional information regarding data coordinating centers is requested in a later section. If your study will develop in phases, address each item below by phase.

A. **Recruitment Process:**

1. Describe how you will identify, approach, and inform potential participants about your study. Include details about who will perform these activities and what their qualifications are.

IRB-approved recruitment information will be posted and distributed throughout the campuses of the Johns Hopkins University, including the Schools of Public Health, Medicine and Nursing as well as other locations as allowed in the greater Baltimore area. In addition, the CIR has ongoing recruitment using IRB-approved advertising (electronic and/or other media publications and advertising), social media, an IRB-approved screening protocol (H.22.02.04.19. A2), and a large data base of former CIR clinical trial participants and initial contacts that we can query for potential recruits.

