The data will be analyzed using the computer software STATA (version 13, Stata Corp, College Station, TX). Each participant will serve as her own control. Summary data of the baseline characteristics of participants will be described using mean (SD) and median for continuous variables or frequencies and proportions for categorical data, as appropriate. Vaccine HAI titers will be measured prior to vaccination (day 39) and at 17 days following vaccination (day 56)

PA1: To determine if vaccination with IIV prior to ovulation (day 11 of menstruation) is associated with changes in post-ovulation serum reproductive (progesterone and estradiol) hormone concentrations.

-H 1: Post-vaccination serum reproductive hormone concentrations will be lower in the post-vaccination cycle than measured prior to vaccination.

The skewness of the hormone concentration distributions will be checked using Kolmogorov-Smirnov test or Shapiro-Wilks test. Transformation of the non-normal data to achieve normality will be attempted using natural logarithms or other mathematical functions. In the event that power transformations fail to normalize the data then non-parametric tests will be used. The mean difference (SD) between pre-vaccination serum hormone (progesterone and estradiol) concentrations and post-vaccination serum hormone concentrations measured during the luteal phase (days 17, 21, 28) of menstruation for each participant will be estimated using paired t-test for parametric data or by the Wilcoxon matched-pairs signed rank sum test for non-parametric data. A p-value < 0.05 will be considered statistically significant in all analyses. Stratified analyses will be conducted to determine if host characteristics modify the effects of vaccination on hormonal responses.

EA1: To determine if serum inflammatory biomarker (cytokines, chemokines, and C-reactive protein) concentrations differ following vaccination with IIV.

-H2: Serum pro-inflammatory biomarker concentrations at 24- and 48-hours post vaccination will be increased relative to baseline concentrations.

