The skewness of the cytokine concentration distributions will be checked using Kolmogorov-Smirnov test of normality. Transformation of the non-normal data to achieve normality will be attempted using natural logarithms. In the event that natural logarithm transformation fails to normalize the data then non-parametric tests will be used. Relationships between the different inflammatory biomarkers interest will be analyzed using Pearson's correlation or with Spearman's rank test, as needed. The mean difference (SD) in cytokine concentrations between baseline and at 24 hours post-vaccination, and between baseline and 48 hours post-vaccination within individuals will be evaluated by paired t-test for parametric data or by the Wilcoxon matched-pairs signed rank sum test for non-parametric data. Stratified analyses will be used to determine if host characteristics

modify the effects of vaccination on hormonal responses. Our study design will also allow us to look at differences in cytokines at various points in the nonvaccination menstrual cycle.

EA2: To determine if post-vaccination inflammatory biomarker responses to IIV receipt (days 40 and 41) are associated with changes in reproductive hormone levels during the second menstrual cycle.

-H3: Changes in serum pro-inflammatory responses between baseline and 24(and/or 48)-hours post-vaccination, will be inversely correlated with serum reproductive hormone concentrations during the second menstrual cycle.

Correlations between changes in post-vaccination serum pro-inflammatory biomarkers (days 39 to 40, 39 to 41) and changes in serum hormone responses during the second menstrual cycle (days 45 to 49, 45 to 56), will be calculated using Pearson's correlation coefficient and evaluated using the paired t-test for parametric data or Spearman's rank correlation test and the Wilcoxon matched-pairs signed rank sum test for non-parametric data. In addition, we will correlate changes in the hormone levels observed in the second cycle to the first cycle (days 17 to 21, 17 to 28) using the same analytical techniques.

EA4: To describe the frequency of adverse events in the 7 days after vaccination, including fever, myalgia, malaise, and hypersensitivity reactions, and to determine if these adverse events are associated with cytokines responses.

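### EA1 tests cytokine change within the vaccinated cycle only; a between-cycle contrast using control samples already scheduled should be added beside it

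*Protocol*

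**What the plan says.** All references are to the Protocol unless stated.

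- **Hypothesis (data analysis plan, EA1, H2):** "Serum pro-inflammatory biomarker concentrations at 24- and 48-hours post vaccination will be increased relative to baseline concentrations".
- **Test (EA1):** the "mean difference (SD) in cytokine concentrations between baseline and at 24 hours post-vaccination, and between baseline and 48 hours post-vaccination within individuals", by paired t-test or Wilcoxon signed rank test.
- **Meaning of baseline:** EA1 gives none. The Day 39 visit applies the word to the cytokine sample taken before vaccination, and EA2 defines biomarker change as Day 39 to 40 and Day 39 to 41. Section III.A uses the word differently: the plan is to "measure their cytokines and reproductive hormones for 1 month to establish a baseline".
- **Unvaccinated-cycle samples:** the schedule table and visit list place cytokine draws on Days 11, 12 and 13. Their stated use is the last sentence of EA1: "Our study design will also allow us to look at differences in cytokines at various points in the nonvaccination menstrual cycle". It names no test and no comparison with the vaccinated cycle.
- **Own-control principle:** the analysis plan opens with "Each participant will serve as her own control". PA1 applies this across cycles for progesterone and estradiol.
- **Pilot:** according to the Background, "cytokine levels were not assessed during the baseline menstrual cycle without vaccination". The planned 90 women include those in the pilot (sample size text under Participants): "this includes the 30 women enrolled in the pilot study".
- **SAP:** it contains the progesterone power calculation and nothing on cytokines.

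**The concern.** A before-after test measures everything that changes between the two draws. Here the draws fall just before ovulation, over one to two days, with repeated clinic visits. If a marker moves over those days for reasons unrelated to vaccine, the EA1 test registers that movement together with any vaccine response. The unvaccinated cycle is where the movement could be seen, and the schedule now collects the samples that the pilot lacked.

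What is at stake is interpretation. An exploratory objective is to find the best biomarkers of the inflammatory response after vaccination, and the plan calls p < 0.05 significant in every analysis. A marker could be put forward on a before-after change that the unvaccinated cycle also shows. Writing the comparison now also avoids choosing its form after results on 15 or more markers are known.

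**Working it through.** **1. Which comparison EA1 makes.** If baseline meant the unvaccinated month (Section III.A), EA1 would compare levels between cycles. The Day 39 label and EA2's Day 39 to 40 and 39 to 41 changes favour the within-cycle reading. That is the natural reading, though EA1 does not state it.

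**2. The plan's own figure.** No power figure is given for EA1. The only one is for progesterone, and it serves here to fix the method. For a median ratio of 0.70 and correlation 0.60, the SD of the difference is √(0.51² + 0.54² − 2 × 0.60 × 0.51 × 0.54) = 0.470. The effect is |log10 0.70| = 0.155, and with n = 90 the noncentrality is 0.155 / (0.470/√90) = 3.12. Two-sided paired-t power at 0.05 is 0.87, against 0.86 stated. The calculations below therefore use a two-sided paired t-test at 0.05. The progesterone figures neither support nor weaken the EA1 point.

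**3. Sensitivity of the one-cycle test to drift.** Assumptions: no vaccine effect; drift d in units of the SD of the within-woman change. The documents give no drift, SD or correlation for cytokines. Rejection probability comes from the noncentral t with noncentrality d√n and n − 1 degrees of freedom.

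| Assumed drift (SD) | n = 60 | n = 90 |
|---|---|---|
| 0 | 0.05 | 0.05 |
| 0.05 | 0.07 | 0.08 |
| 0.1 | 0.12 | 0.16 |
| 0.2 | 0.33 | 0.47 |

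The n = 90 column assumes that the pilot women have comparable 24 h and 48 h draws, which the documents do not state. H2 is directional (an increase), so these are rates of false support for H2 only if the drift is upward. If it is downward, wrongly significant increases occur in under 1% of cases (0.0096 at 0.05 SD and 0.0032 at 0.1 SD, n = 60).

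**4. What a contrast would do.** For each woman, take the vaccinated-cycle change minus the unvaccinated-cycle change. If drift is the same in both cycles it cancels, and the error rate stays at about 0.05 (simulated at n = 60: 4.9% with drift 0.2 SD, 5.0% with 0.3 SD). If some drift is left over, it does not cancel: a residual 0.1 SD gives rejection in 8-10% of cases and 0.2 SD in 19-25% (n = 60, assumed correlation r of the two changes 0 to 0.3).

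**5. Its precision.** The women available number at most 90 − 30 = 60, because the pilot has no unvaccinated-cycle cytokines. The SD of the contrast is √(2(1 − r)): 1.414 at r = 0 and 1.183 at r = 0.3.

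- One-cycle test, n = 60, 80% power: 0.368 SD.
- Contrast, n = 60: 0.368 × 1.183 = 0.44 SD to 0.368 × 1.414 = 0.52 SD.
- At a true effect of 0.368 SD, contrast power is 0.66 (r = 0.3) to 0.51 (r = 0).
- With only one further season (30 women): 0.63-0.75 SD for the contrast, against 0.53 SD for the one-cycle test.

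**6. Pairing of draws.** Day 11 has a window of ±2 days; Days 12 and 13 are listed with none and are not tied to the actual Day 11 draw. A Day 11 draw taken on Day 9, 10, 11 or 12 puts the Day 12 draw 3, 2, 1 or 0 days later. In the vaccinated cycle, Day 40 ±1 allows 0 to 2 days after Day 39. This does not affect EA1 as written, but a contrast needs pairing by actual elapsed time.

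**The case against.** The strongest reply is that EA1 and H2 make statements about time order: do concentrations differ, or rise, after vaccination? A before-after test answers exactly that. EA1 is exploratory, the text answers a form item that asks for a brief analysis plan, and the team added the unvaccinated-cycle draws and foresaw looking at them. All of this stands, and it limits the weight of the point. It does not supply the comparison: the foreseen look is within the unvaccinated cycle.

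A reader might infer that EA1 would credit any change to the vaccine, or that its positive findings would be false. The documents support neither. No sentence commits the team to attribution, no drift is reported, and at 0.05 SD the error is near nominal.

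A reader might also infer that the contrast should decide which markers count as vaccine responses. That goes too far. At the effect that the one-cycle test detects with 80% power, the contrast has power of only 0.51-0.66, so without drift a third to a half of such true responses would be denied. Section V lists 15 markers without limiting the list to them; at two times that is about 30 unadjusted comparisons.

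Finally, women vaccinated in their first study cycle are imperfect controls. The Background reports IL-8 and TNF-α lowered at 14 and 28 days after inactivated vaccine, and their control Day 11 comes about 28 days or more after vaccination (39 − 11 = 28). A stable shift cancels in a change score; a resolving one does not.

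**Conclusion.** The point holds in limited form. On its natural reading, EA1 tests change within the vaccinated cycle only, and neither document writes a between-cycle cytokine contrast, although the control samples are scheduled and PA1 compares cycles for hormones. The test cannot by itself distinguish a vaccine response from a change that those visits would show anyway.

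The size of the problem is unknown. The 12% and 33% rejection rates at n = 60 rest on assumed drifts of 0.1 and 0.2 SD; they show sensitivity and are not evidence that drift exists. This is a low-cost improvement to an exploratory analysis. It does not touch the primary hormone comparison.

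**What to change.** Keep the one-cycle test and add the following to EA1.

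- State that baseline for the one-cycle test is the draw on the day of vaccination, if that is what is meant.
- For each marker, estimate on the log scale, within woman: the 24 h or 48 h change from the vaccination-day draw, minus the change over the same elapsed time from the Day 11 draw in the unvaccinated cycle.
- Define cycles by vaccination status, not day number, so that women with flipped order are handled correctly. Pair draws by actual elapsed time, with the analysis window set in advance, and report how many women meet it.
- Report the contrast and its 95% CI beside the one-cycle result, labelled exploratory and unadjusted for multiple markers. Word any attribution to vaccine in light of both results, with no pass/fail gate.
- Show results with and without women vaccinated in their first study cycle, whose control cycle may not be free of vaccine effect.
- State that the contrast removes only drift common to both cycles.

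The cost is analysis wording and precision; no sample is added. The contrast excludes the 30 pilot women and, even with both further seasons enrolled, detects about 0.44-0.52 SD against 0.37 SD for the one-cycle test in the same 60 women. Without drift the one-cycle test is the more powerful, which is why it should stay.

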
Primary Objectives:

1. To explore whether receipt of IIV during the second week of the menstrual cycle (i.e., the week prior to ovulation) is associated with changes in steroid hormone levels, particularly decreases in progesterone, following ovulation.
2. To assess the feasibility of conducting further research in this area.

Primary Endpoints:

1. Changes in levels of estradiol and progesterone one week after receipt of influenza vaccination.

Exploratory Objectives:

1. To explore whether inflammatory cytokine responses to IIV receipt are associated with changes in reproductive hormone levels.
2. Identify optimal biomarkers of the inflammatory response after vaccination.
3. To collect peripheral blood mononuclear cells (PBMC) for future studies of cellular immune response.

Exploratory Endpoints:

1. Assess the inflammatory cytokine responses (including C-reactive protein [CRP]) to IIV.
2. To record adverse events in the 7 days after vaccination, including fever, myalgia, malaise, and hypersensitivity reactions.

II. Background and Rationale: Explain why this study is being done. Summarize briefly what is already known about the issue and reference previously published research, if relevant.

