1. Obtain blood for measurement of cytokines.

Day 17 +/-2 days (after ovulation), Day 21 +/- 2 days

Day 28 +/- 5 days (1st day of menstrual cycle)

1. Collect brief history of any new illnesses or problems since last visit
2. Review pregnancy prevention counseling.
3. Obtain blood for measurement of progesterone, and estradiol.

Day 21 +/- 2 days:

1. Collect approximately 30 cc of blood for PBMC processing.

Day 38-45

1. Participant to utilize LH strip at home, and call study staff when positive.
2. Participant to record on memory card results of LH strip.

Day 39 +/- 3 days (~ 11 days after menstruation; prior to ovulation)

1. Collect brief history of any new illnesses or problems since last visit
2. Review pregnancy prevention counseling.
3. Obtain blood for measurement of progesterone, estradiol, baseline cytokines and Hemagglutination Inhibition Assay (HAI).
4. Obtain approximately 30 cc of blood for PBMC processing.
5. Check urine pregnancy test.
6. Vaccinate subject with IIV.

Day 40 +/-1 day (1 day after vaccination), Day 41 +/-1 day (2 days after vaccination)

1. Collect brief history of any new illnesses or problems since last visit, ask about adverse events after vaccination.
2. Review pregnancy prevention counseling.
3. Obtain blood for measurement of cytokines.
Days 41-43 (2-4 days after vaccination).

Subject to answer questions reactivity in the REDCap database or on the memory card.

Day 45 +/-1 day (6-8 days after vaccination), Day 49 +/- 1 day (10-12 days after vaccination)

1. Collect brief history of any new illnesses or problems since last visit; ask about adverse events after vaccination.
2. Review pregnancy prevention counseling.
3. Obtain blood for measurement of progesterone, and estradiol.

Day 49 +/- 1 day (10-12 days after vaccination)

1. Obtain approximately 30 cc for PBMC processing.

Day 56 +/-4 days (1st day of menstruation)

1. Get brief history of any new illnesses or problems since last visit.
 2. Check urine pregnancy test.
 3. Obtain blood for measurement of progesterone, estradiol and for HAI.
3. Describe the expected duration of the study from the perspective of the individual participant and duration overall.

Each participant will spend about 3-4 months in the study, from screening to completion.
Each subject will be expected to come to approximately 14 visits

4. Provide a brief data analysis plan and a description of variables to be derived.

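### EA2 tests its correlations with a paired t-test, which does not test association, and measures hormone change only from Day 45, so an inverse link already present then can cancel or change sign

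*Protocol*

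**What the plan says.** All of EA2 is in the Protocol, Study Implementation item 4 (data analysis plan). The SAP holds only the power calculation for the primary aim, so it neither repeats nor corrects EA2.

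- **Aim.** EA2 asks whether biomarker responses on Days 40 and 41 "are associated with changes in reproductive hormone levels during the second menstrual cycle".
- **Hypothesis H3.** Biomarker changes "will be inversely correlated with serum reproductive hormone concentrations during the second menstrual cycle".
- **Variables.** Biomarker change runs from Day 39 to 40 and from Day 39 to 41. It is correlated with "changes in serum hormone responses during the second menstrual cycle (days 45 to 49, 45 to 56").
- **Test.** Parametric branch: Pearson's "correlation coefficient and evaluated using the paired t-test for parametric data". Non-parametric branch: Spearman's rank correlation test together with the Wilcoxon matched-pairs test.
- **Between cycles.** "In addition, we will correlate changes in the hormone levels observed in the second cycle to the first cycle". The windows for the unvaccinated comparison, and the method, are then stated as ("days 17 to 21, 17 to 28) using the same analytical techniques".

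The visit list places the later samples at "Day 45 +/-1 day (6-8 days after vaccination), Day 49 +/- 1 day (10-12 days after vaccination"). The primary endpoint is "Changes in levels of estradiol and progesterone one week after receipt of influenza vaccination", which is about Day 45. The Protocol's opening summary reports the pilot's non-significant 20% fall in progesterone at the matching day 17. The NOTE in Study Implementation allows the two cycles to be swapped.

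**The concern.** EA2 is the planned analysis of exploratory objective 1, the mechanism that motivates the study: does a stronger cytokine response go with a hormone change?

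Two things stand in the way. First, the p-value named for the parametric branch answers a different question. The plan tries to transform the data to normality before it falls back on ranks, so that branch is the one it aims for. Second, the hormone variable subtracts the Day 45 value. That is the time at which the trial looks for its primary effect and at which the pilot saw its fall. If the cytokine-related effect has already happened by then, a change measured from Day 45 removes it. H3 speaks of concentrations and the analysis uses later changes, so hypothesis and analysis do not match.

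There is also a smaller labelling problem. When the order is swapped, the second menstrual cycle is the unvaccinated one, and EA2's wording then points to the wrong cycle.

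**Working it through.** The documents give no power or expected correlation for EA2, so there is no planned figure to reproduce.

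**Inputs from the Protocol (section III.B) and SAP.** SD of log10 luteal progesterone is 0.54 in the vaccinated cycle and 0.51 in the unvaccinated cycle, and the correlation between cycles is 0.60. I assume these hold at each luteal visit. The target of 90 women includes 30 from the pilot, so I use n = 60 (90 - 30) to n = 90 complete pairs.

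**Assumed, not in the documents.** The correlation r between cytokine change and Day 45 log progesterone is -0.20 to -0.40. The within-cycle correlation w of the remaining hormone variation is 0.60 to 0.85. The effect at Day 49 is k times that at Day 45. Cytokine change is unrelated to unvaccinated-cycle hormone. Tests are two-sided at 0.05, with power by Fisher's z unless stated.

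**Step 1: what the paired t-test responds to.** The statistic is mean(X - Y) / [SD(X - Y)/√n]. Its numerator holds only the two means. The correlation enters only through the SD.

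- No association, unit SDs, means +0.3 and -0.3: the noncentrality is (0.6/√2)√n, which is 3.29 at n = 60 and 4.02 at n = 90. The paired t-test is significant in 90% and 98% of trials; a test of r is significant in 5%.
- r = -0.30 and equal means: the paired t-test is significant in 5%. A test of r has power 65% and 82%.

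The Wilcoxon signed-rank test likewise responds to a difference in location, not to association.

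**Step 2: the Day 45 window.** Let X be the standardised cytokine change and b = 0.54r its slope at Day 45. Then

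cov(X, H49 - H45) = (k - 1)b

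corr = (k - 1)b / √[(k - 1)²b² + 2(0.54² - b²)(1 - w)]

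Example with r = -0.30, k = 0, w = 0.60: b = -0.162, and corr = 0.162/√(0.0262 + 0.2123) = +0.33.

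| Effect by Day 49 | Correlation with Day 45 to 49 change | Significant result |
|---|---|---|
| Unchanged (k = 1) | 0 | inverse, 2.5% |
| Half faded (k = 0.5) | +0.11 to +0.37 | wrong sign, 14% to 95% |
| Gone (k = 0) | +0.22 to +0.62 | wrong sign, 40% to over 99% |
| Doubled (k = 2) | -0.22 to -0.62 | inverse, 40% to over 99% |

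At r = -0.30 alone, half faded gives +0.17 to +0.28 (26% to 75%) and gone gives +0.33 to +0.50 (74% to over 99%). The Day 45 to 56 change has the same sign pattern.

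**Step 3: does the first-cycle comparison rescue it?** No. Its windows start at Day 17, the counterpart of Day 45, and it involves no biomarker. Even if the Day 17 to 21 change were subtracted, the covariance with X would stay at (k - 1)b.

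**Step 4: matched-visit alternative.** Var(H45 - H17) = 0.54² + 0.51² - 2(0.60)(0.54)(0.51) = 0.2212, so the SD is 0.470.

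- Difference: r = 0.54r₄₅/0.470, where r₄₅ is the assumed Day 45 correlation. This gives -0.23, -0.34 and -0.46 for -0.20, -0.30 and -0.40. Power runs from 42% (n = 60, weakest) to over 99%; at -0.30 it is 77% to 92%.
- Day 45 adjusted for Day 17: partial r = r₄₅/√(1 - 0.36), from -0.25 to -0.50. Power is 48% to over 99%.

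**The case against.** **The test is a slip of wording in one branch.** The plan still names Pearson's coefficient. Elsewhere it relates biomarkers to each other by Pearson or Spearman with no paired test attached, and Spearman's test in the non-parametric branch is valid. That is fair: a reader who concluded that EA2 has no valid test at all would go too far. But as written, the parametric correlations are evaluated by the paired t-test, and nothing in either document corrects it.

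**The between-cycle sentence may be sound.** If "In addition, we will correlate changes in the hormone levels observed in the second cycle to the first cycle" loosely means comparing same-unit hormone changes between cycles, a paired t-test or Wilcoxon test is suitable and only the verb is wrong. If it means a correlation, the fault carries over. The text supports either reading, so the point is conditional.

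**Within-cycle change is a legitimate variable.** Exploratory objective 1 and the EA2 aim both speak of changes; only H3 speaks of concentrations. This stands as a choice of what to estimate. It does not remove the mismatch with H3, and the plan does not say that this choice leaves out any effect complete by Day 45.

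**The harsh figures need harsh assumptions.** A high rate of wrong-sign results needs a sizeable link that fades substantially by Day 49. This is right, which is why weaker correlations and partial fading are shown. At r = -0.20 and half faded, the wrong-sign rate is 14% to 41%, and power for the matched difference is only 42% to 59%.

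**Conclusion.** Both points hold. The choice of test is wrong as written and depends on no assumption: a paired t-test is not a test of correlation. The window point is a possibility. An inverse link present at Day 45 cancels if it persists unchanged and reverses if it fades; one that grows or first appears later keeps its inverse sign.

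A reader might infer that EA2 will come out null or reversed. The documents do not support that, because they give no time course and no expected correlation. Nor do they support the inference that the primary hormone comparison is compromised: it uses paired tests for mean differences, which is their proper use. The sizes above are illustrations that rest on the assumed r, w, k and mean changes. EA2 is exploratory, but it is the only planned analysis of exploratory objective 1, so it should be corrected before the data are analysed.

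**What to change.** 1. Evaluate every EA2 correlation by the test and 95% confidence interval of the Pearson or Spearman coefficient. Keep the paired t-test or Wilcoxon test only for a separately stated comparison of same-unit hormone values or changes between cycles. Reword the between-cycle sentence to say which is meant.
2. Make the main EA2 hormone variable log hormone in the vaccinated cycle minus log hormone in the unvaccinated cycle at the matched visit: Day 45 minus 17, 49 minus 21 and 56 minus 28. Put Day 45 minus 17 first, because it matches the primary endpoint. Align the EA2 and H3 wording with this variable. Keep the Day 45 to 49 and 45 to 56 changes as secondary, and state that they detect only an effect that changes after Day 45.
3. Label the cycles vaccinated and unvaccinated instead of first and second, so that the wording also holds when the order is swapped.

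The cost is analysis wording. The current schedule already takes hormone blood at all six visits. The downside is a few more exploratory correlations, which should be reported as exploratory with no multiplicity-controlled claim.
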